### 8.1 Clinical Study Protocol C-SY 00093

A multicenter clinical study was conducted at four sites in Israel in 2017. Sixty-Six subjects were enrolled (40 Men (61%) and 26 Women (39%), BMI <40), of which three failed to ingest the capsule, including one subject with a known swallowing disorder which was not disclosed to the study team during screening. Forty-Three had polyp(s) (65%) as indicated by their prior recent colonoscopy reports and the other 23 were considered as average risk population without any prior information about their colon.

All study procedures were completed and feedback from most subjects was positive and reassuring that the procedure was well-tolerated.

All capsules (except one) were collected and retrieved for QA inspection. They were all found to be intact and hermetically sealed.

The total transit time (TTT) is measured in hours between capsule ingestion to excretion. The TTT is the sum of 3 distinct sections:

- Time until reaching the caecum
- Time capsule dwells in the caecum
- Time of colon passage until excretion

The following table is the summary of all 63 cases in whom the study was completed (3 did not ingest). The standard deviation (STD) is quite high due to the considerable variability in bowel motility.

	Total Transit Time	Time to Caecum	Time in Caecum	Passage in colon
Average (hours)	52.3	15.9	16.8	16.5
STD	32.9	13.7	18.8	12.1

Table 2: Average transit time of the 3 sections of the GI tract and the standard deviation in each one.

There were no cases of C-Scan capsule retention (medical definition of Capsule retention is when TTT is longer than 300 hours – about 13 days).

The C-Scan is designed to operate continuously for 100 hours. There was one case in which the capsule was retained for 100-200 hours and then removed during the follow-up colonoscopy procedure

	Document Title	Clinical Investigational Plan For Study CL-SY-02-0096		
	Document No.	DOC001593	Revision	03

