### 10.3 Primary Safety Outcome Measure

The safety of the Check-Cap System will be evaluated by the incidence of device or procedure related Serious Adverse Events (SAE), as adjudicated by the Independent Physician Adjudicator.

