### 12.3 Exclusion Criteria

- a. Subject who is not a suitable candidate for a colonoscopy (i.e., moderate sedation)
- b. Known history of dysphagia or other swallowing disorders.
- c. History of the followings: Inflammatory Bowel Disease (IBD) including Crohn's disease or Ulcerative, Colitis, Meckel's Diverticulum, Bowen Hernia, known fistulas or strictures (doctors' discretion), or a history of small bowel obstruction.
- d. Known motility disorders:
  - i. Chronic Constipation: less than 3 bowel movements/week, w/out the use of laxatives.
  - ii. Delayed gastric emptying.
  - iii. Narcotic use
- e. Prior history of abdominal surgery that might cause bowel strictures leading to capsule retention, as determined by physician discretion with the exception of appendectomy, cholecystectomy and hysterectomy
- f. Any condition believed to have an increased risk for capsule retention, strictures, bowel adhesion or other obstacles to free passage of the capsule (such as intestinal tumors, radiation enteritis) or incomplete colonoscopies (e.g. due to obstructions or NSAID enteropathy) as determined by physician discretion.
- g. Has a cardiac device (e.g. pacemaker or ICD) or any other active implanted device
- h. Known sensitivity to iodine, or with known kidney failure.
- i. Known condition which precludes compliance or is contraindicated with study and/or device instructions.
- j. Has a Magnetic Image Resonance (MRI) procedure scheduled within 1 month
- k. Known condition of drug abuse and/or alcoholism.
- l. Women who are either pregnant or nursing at the time of screening (to be verified by urine or serum pregnancy test for woman of child- bearing potential who are not post-menopausal or undergone surgical sterilization.
- m. Concurrent participation in another clinical trial using any investigational drug or device.

	Document Title	Clinical Investigational Plan For Study CL-SY-02-0096		
	Document No.	DOC001593	Revision	03

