## 12.4 Withdrawal Criteria

Subjects may withdraw from the study at their own request at any time.

The investigator may withdraw a subject from the study at any time for the following reasons:

- a. Severe side effects clearly related to the study device or procedure
- b. Less than adequate compliance with the study routine
- c. Presence or appearance of exclusion criteria
- d. Refusal to undergo 'post' colonoscopy
- e. A significant protocol violation
- f. At the specific reasonable request of the sponsor

The sponsor must be informed in each withdrawal case within 24 hours. The reason for withdrawal has to be recorded in the subject's file.

CONFIDENTIAL

The information contained in this document is confidential and the sole property of "Check-Cap"  
Any reproduction in part or whole without the written permission of "Check-Cap" is prohibited

	Document Title	Clinical Investigational Plan For Study CL-SY-02-0096		
	Document No.	DOC001593		Revision 03

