### 13.5 Visit 1: Baseline

Upon completion of the informed consent process, subject's eligibility will be assessed against the Inclusion and Exclusion criteria. Previous reports of optical or virtual colonoscopy should be collected and kept with the subject's file.

If the subject does not meet the inclusion/exclusion criteria, they will be considered a screen failure and excluded from the analysis.

The following information will be collected at this visit:

- General medical history and concomitant medication will also be assessed and documented.
- Subject's demographic and baseline information will be assessed and documented, including: date of birth, gender, height, weight, belly circumference, prior abdominal surgery, GI symptoms, and reason for referral.
- If applicable, documentation of previous GI procedures, such as optical colonoscopy

	Document Title	Clinical Investigational Plan For Study CL-SY-02-0096		
	Document No.	DOC001593	Revision	03

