## 14 STATISTICAL ANALYSIS

### 14.1.1 Sample Size Considerations

This is a pilot safety study; therefore, sample size is not determined by power analysis. Up to 45 subjects will be recruited to the study.

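### Withdrawal criterion c has no cut-off at ingestion, so a delayed capsule can itself take a subject out of safety data collection and the primary count

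*Combined protocol and SAP*

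**What the plan says.** Section 12.4 introduces its list with "The investigator may withdraw a subject from the study at any time for the following reasons", and item c is "Presence or appearance of exclusion criteria". It then asks for two things only: that the sponsor be told within 24 hours and that the reason be filed. It does not say what happens to the subject's data or safety follow-up.

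Exclusion f in 12.3 is "Any condition believed to have an increased risk for capsule retention, strictures, bowel adhesion or other obstacles to free passage of the capsule". It gives intestinal tumours as an example and rests on physician discretion. It is not confined to conditions already known.

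Section 13.5 places the eligibility check at baseline: "Upon completion of the informed consent process, subject's eligibility will be assessed against the Inclusion and Exclusion criteria". Of those who do not qualify it says "they will be considered a screen failure and excluded from the analysis". Ingestion follows in 13.5.1, as part of the same visit.

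The primary outcome (10.3) is "evaluated by the incidence of device or procedure related Serious Adverse Events (SAE), as adjudicated by the Independent Physician Adjudicator". Section 15.1.3 calls excretion delayed after 100 hours, and counts retention as a serious adverse event once 300 hours have passed. Section 14.1.2 restricts the primary safety set to subjects whose C-Scan procedure was done per protocol, a term it does not define. On size, 14.1.1 states "This is a pilot safety study; therefore, sample size is not determined by power analysis", with at most 45 subjects.

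**The concern.** An eligibility criterion should depend only on what is known before exposure. Here one criterion can be met by information that the exposure produces. If a capsule stalls, imaging or examination may suggest an obstacle to passage. The physician may then judge that exclusion f applies, and criterion c allows withdrawal on that ground. The subject leaves on eligibility grounds, but the reason arose from the safety outcome.

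Two losses could follow. The subject may be treated as not per protocol and left out of the denominator. More seriously, study data collection may end before the 300-hour definition is reached, so that the event is never recorded. Redefining the analysis set alone would not repair the second loss. In a single-arm study whose purpose is to show safety, both push the reported rate down.

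**Working it through.** The plan's own figure of 45 has no alpha, power, target rate or margin behind it, so there is no calculation to reproduce. The check compares the text along the subject's timeline and then gives the scale.

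**Timeline**

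- Hour 0: eligibility has been checked (13.5) and the capsule is swallowed (13.5.1).
- About 100 hours: if the capsule has not been passed, the subject contacts the clinic and abdominal X-ray may follow (13.9, 15.1.3.1). An obstacle could be suspected from this point.
- Any time: withdrawal under criterion c is allowed (12.4).
- More than 300 hours: retention becomes a serious adverse event (15.1.3).
- Window: 300 − 100 = 200 hours in which withdrawal can precede the event.

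**Which criteria can be met after ingestion**

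- Exclusion f: yes. It is open-ended and turns on belief about retention risk.
- Exclusion b (swallowing): only where a known disorder existed and was not disclosed. Section 8.1 reports such a subject in the preceding study: "three failed to ingest the capsule, including one subject with a known swallowing disorder which was not disclosed to the study team during screening".
- Exclusions c and d: tied to history or to known conditions, so a stricture first found because of the capsule does not strictly meet them.

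**How likely is delayed passage?** Section 8.1 reports four transits longer than 120 hours. The denominator is not given with that figure, so I assume the 63 completed cases.

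- Rate: 4/63 = 6.3%
- Expected among 45: 45 × 4/63 = 2.9
- Probability of at least one: 1 − (59/63)^45 = 0.95

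Delayed passage is therefore likely to occur. Retention beyond 300 hours is another matter, since 8.1 reports none.

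**Effect of losing one event** (exact Clopper-Pearson limits)

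- One related event kept: 1/45 = 2.2%, 95% CI 0.06% to 11.8%
- The same subject removed: 0/44 = 0%, upper limit 1 − 0.025^(1/44) = 8.0%

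**Range for the unknown share.** Let p be the true related-event rate and w the share of affected subjects withdrawn under c and not counted. The expected reported rate is p(1 − w)/(1 − pw). Both p and w are assumptions.

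| p | w = 0 | w = 0.25 | w = 0.5 | w = 1 |
|---|---|---|---|---|
| 2% | 2.0% | 1.5% | 1.0% | 0% |
| 5% | 5.0% | 3.8% | 2.6% | 0% |

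At p = 5%, the chance of reporting no event among 45 subjects, (1 − p(1 − w))^45, rises from 0.10 at w = 0 to 0.32 at w = 0.5.

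**The case against.** The best defence is that the plan nowhere says data stop at withdrawal. Withdrawal is optional. The schedule requires at least two calls a day until the capsule is out, 13.9 commits site staff to ensuring excretion, 15.1.3.1 has the clinic initiate contact if needed, and 16.3 requires every adverse event to be recorded. None of these is limited to subjects still in the study. That stands as far as it goes, and clinical care is not in doubt. But none of these provisions mentions withdrawn subjects either, so whether study data collection and counting continue is left open.

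A second defence is that a safety set of everyone in whom ingestion was attempted would cure the bias whatever 12.4 says. That is right for the denominator, but not for an event that was never collected.

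A reader might also infer more than the text supports:

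- That subjects are reclassified as screen failures after swallowing the capsule. The rule in 13.5 belongs to the baseline check before ingestion, and no text extends it further. What is missing is an explicit limit.
- That several exclusion criteria can be triggered by the outcome. Only f clearly can. Narcotic use is listed under known motility disorders, and no exclusion criterion concerns pain.
- That the preceding study shows such reclassification. It does not. It kept the subject with the undisclosed disorder among both its 66 enrolled and its three failed ingestions, and it does not say when the disorder came to light. Failed ingestion is also not the primary outcome.

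**Conclusion.** The point holds in a limited form. Criterion c applies exclusion criteria after ingestion, exclusion f can be revealed by a held-up capsule, and nothing keeps a subject so withdrawn in safety data collection or in the primary count. Followed as written, the plan can lose a primary-outcome event because of that outcome.

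This is a permitted path, not a certain one, and the documents give no basis for estimating how often it would be taken. Its size is best shown by one lost event: 1/45 (2.2%) becomes 0/44 (0%). That assumes the event would be adjudicated as related and that the subject is dropped from both numerator and denominator. Because the analysis is descriptive (14.1.4), no planned step would reveal the loss. The ambiguity should be closed before enrolment.

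**What to change.** 1. In 13.5, state that screen failure with exclusion from the analysis applies only to subjects found ineligible before ingestion is attempted.
2. In 12.4, state that an exclusion criterion found or arising after that point is recorded as an eligibility deviation or a new event, and removes neither the subject nor their adverse events from the safety set. Define that set in 14.1.2 as all subjects in whom ingestion was attempted, so that the two sections agree.
3. In 12.4, state that safety data collection for withdrawn subjects continues, subject to their consent, until excretion is confirmed and Follow-up 2 is done. List withdrawals by reason in the report.

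Clinical handling stays with the investigator; these changes concern only data collection and counting. The cost is a few sentences, some extra follow-up contacts of a kind already scheduled, and a safety rate that may look less favourable.

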## 13 STUDY PROCEDURES AND SCHEDULE

### 13.1 Study Procedures

The C-Scan study procedures and flow are outlined in Figure 3. The schedule of study assessments are listed in Table 1. The subjects are only required to attend two visits, but are expected to conduct phone assessments after ingestion but prior to expulsion of the capsule.

*Table 1: Schedule of Assessments*

Assessments	Pre-screening	Visit 1: Baseline and C-Scan	Follow-up 1: C-Scan - During Procedure follow-up	Follow-Up 2: C-Scan Procedure End follow-up Call	Follow-up 3: Colonoscopy Post Procedure follow-up Call
Visit Window	-30-0 days	0 days	0- As required days	1-3 days post procedure	1-3 days post procedure
Questionnaire	X				
Informed Consent		X			
Inclusion/ Exclusion Criteria		X			
Demographics		X			
Medical History		X			
Concomitant Medications		X			
Pregnancy test 		X			
C-Scan procedure		X			
Connect to C-Scan		X			
C-Scan capsule		X			
Ingest contrast		X	X		
FIT test			X		
Follow up phone calls 			X		
Capsule Excretion				X	
Abdominal x-ray 				X	
Subject Satisfaction Survey				X	X
Boston Bowel Preparation Scale (BBPS)					X
Colonoscopy Report	X 				X
Follow up visit call				X	X
Adverse Events		X	X	X	
Study Exit					X

[figure not shown]
Urine pregnancy test for women of childbearing potential

Minimum of two phone calls per day until capsule excretion

Abdominal x-ray ONLY if suspected that capsule has not been excreted (subject will come to office/unscheduled visit)

Collection of a previous colonoscopy report, if available

	Document Title	Clinical Investigational Plan For Study CL-SY-02-0096		
	Document No.	DOC001593	Revision	03

	Document Title	Clinical Investigational Plan For Study CL-SY-02-0096		
	Document No.	DOC001593	Revision	03

Figure 3: Study Procedure Flow Chart

### 13.2 Study Documentation

The following documents and information will be collected:

- Completed Visit and Follow-up Case Report Forms (CRFs)
- Referring procedure report (optical colonoscopy or virtual colonoscopy), if applicable
- FIT Results (+ photo)
- Subject's diary with all daily activities during home procedure
- Subject's usability questionnaire
- Subject Satisfaction Questionnaire
- C-Scan procedure raw data
- C-Scan report
- Optical Colonoscopy report
- Video recording of Optical Colonoscopy
- Pictures of Optical Colonoscopy, if taken
- Copy of pathology report, if conducted

### 13.3 Prescreening

Potential eligible patients scheduling an optical colonoscopy may be approached regarding participation in this study. Patients will be prescreened may be completed in person or via phone and logged on the Prescreening Log with outcomes regarding potential eligibility.

### 13.4 Informed Consent Process

An explanation of the study device, the study and participation requirements will be provided to each eligible prescreened patient. The informed consent document will be reviewed with each patient and they will be provided time to ask questions. Consent to participate in this study must be given in writing. The signed informed consent will remain in subject's file. A signed copy will be given to the subject.

Informed consent will be obtained prior to any study procedures being conducted. Site will maintain a log with all subjects who signed an informed consent to participate in the trial. The log will include the subject's full name, subject's study code and date of enrollment. Enrollment log will be kept in the site's Regulatory Binder which is maintained in a secure location. The subject is considered enrolled at the completion of the informed consent process

### 13.5 Visit 1: Baseline

Upon completion of the informed consent process, subject's eligibility will be assessed against the Inclusion and Exclusion criteria. Previous reports of optical or virtual colonoscopy should be collected and kept with the subject's file.

If the subject does not meet the inclusion/exclusion criteria, they will be considered a screen failure and excluded from the analysis.

The following information will be collected at this visit:

- General medical history and concomitant medication will also be assessed and documented.
- Subject's demographic and baseline information will be assessed and documented, including: date of birth, gender, height, weight, belly circumference, prior abdominal surgery, GI symptoms, and reason for referral.
- If applicable, documentation of previous GI procedures, such as optical colonoscopy

	Document Title	Clinical Investigational Plan For Study CL-SY-02-0096		
	Document No.	DOC001593	Revision	03

### **13.5.1 C-Scan Procedure**

Subjects will be instructed to skip breakfast or lunch on the day of C-Scan Capsule ingestion to expedite gastric passage. Liquids are allowed.

The subjects will be connected to the C-Scan Track and after successful system's activation (BIT – built in test), the subject will be asked to ingest the C-Scan Capsule with some water, contrast media (GE Omnipaque 350) and non-soluble fiber, in the presence of a physician investigator or designee. The subject will also be provided with an RF watch. A representative of the sponsor will attend the ingestion procedure, as needed to assure proper activation.

Post ingestion, the subject will receive detailed instructions about the daily routine and activities as well as use of the RF watch and then will be discharged home with written instructions on the procedure Instructions for use (IFU), daily diary, FIT kit and capsule return kit.

## **13.6 Follow-Up 1**

### **13.6.1 FIT Procedure**

All subjects will be required to perform FIT procedure using [OC-Light] FIT Kit prior or during the capsule procedure.

The subjects can perform the test at their home, per their convenience, as per package insert instructions, and report the results to study team (photo of the strip with 1-2 lines). Additional guidance will be provided by the site clinical team as required. Alternatively, FIT procedure may be conducted at the clinic, on the day of C-Scan Capsule ingestion. In case of unclear results, the FIT test will be repeated. One positive result in any of the tests will be considered as positive. FIT procedure date and results will be recorded and documented.

### **13.6.2 Capsule Progress Days: Contrast Ingestion, Laxatives and Non-Soluble Fiber**

One the days in which the capsule is progressing within the subject, the subject is required to ingest contrast media (GE Omnipaque 350, FDA approved under NDA 018956) as well as non-soluble fiber supplements. The subject will be required to ingest daily dose (3 X 15 ml) of contrast media, to be consumed three times per day as well a non-soluble fiber 3x/day with normal diet.

The subject will be provided with Laxadin (5 mg tablets) to be ingested according to the doctor recommendation, on an as needed basis. In routine procedures, subjects might be instructed to take 2 X 5 mg tablets 48-72 hours after ingestions (unless the capsule was already excreted).

### **13.6.3 Subject Diary**

All subjects will be required to keep a log ('Subject's Diary') during procedure documenting general activities, contrast media intake, fibers intake, and food consumption, bowel movement, and system visual/auditory indicators.

### **13.6.4 Follow-Up Phone Calls**

During capsule procedure/progress days, the subjects will be contacted by phone several times daily by the site clinical study team or by dedicated external trained personnel to assess the subjects well-being and to monitor for any change or discomfort, subject satisfaction adverse events and procedure progress.

During the call, if a complaint related to the technical functioning of the device is received, subjects may be also monitored by the technical team (either at home or at the clinic), who may need to examine the

	Document Title	Clinical Investigational Plan For Study CL-SY-02-0096		
	Document No.	DOC001593	Revision	03

system or inquire the subjects about the system visual/auditory indicators in order to assure optimal operation of the C-Scan system. If an adverse vent is reported, the caller will notify the site study team and determine the appropriate course of action.

### **13.7 Follow Up 2: Capsule excretion and collection**

#### **13.7.1 Capsule Return**

Capsule procedure is completed upon capsule excretion or system auditory indication of 'End of Procedure'. Subjects will be instructed to inform the study coordinator or designee upon capsule excretion.

The subjects will be provided with a dedicated capsule collection kit, to assist the subjects in collecting the capsule. Subjects will be instructed to retrieve the capsule upon excretion. Return packaging and instructions will be provided. The subject will return with the Kit the diary, the questionnaire and all unused materials.

In case of doubt regarding capsule excretion, and per physician discretion, subjects may be referred to abdominal X-Ray to confirm capsule excretion.

#### **13.7.2 Usability Questionnaire**

Usability questionnaire will be provided with each Kit and the subjects are instructed to answer these questions once the procedure is completed. A question regarding whether the subject has experienced any adverse events will be included.

